### 10.2 ANALYSIS POPULATIONS

The following are the analysis populations:

- Enrolled Population: This is defined as subjects enrolled and/or randomized to either CORI or Conventional manual instrumentation groups. A total of 140 patients will be competitively enrolled and or/randomized in the study across all the sites including the sites in China.
- Safety Population (SAF): This is defined as all subjects who were treated for UKA (include non-randomized subjects in China as CORI is a pre-market

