## 6.5 SURGICAL TECHNIQUE

All study related procedures with CORI must be performed according to the user's manual (Document ID: 500230 CORI Robotics for Knee Arthroplasty for Australia, Hong Kong, South Korea, and New Zealand, as well as Investigator's Brochure for China) and according to the according to the surgical technique and IFU of the specific S+N Implant System.

Surgeons selected to participate in this study will be familiar with CORI and have written evidence of training and expertise in the study procedure. The Surgeon will conduct Pre-study in order to establish the expertise of the individual surgeons. The exact number of pre-study cases may be adjusted depending on the level of the individual experience of the surgeon.

CORI Case Reports Forms of the non-randomized cases will be collected as proof of surgeons' experience and for inclusion in the safety analysis set (applicable only at sites in China).

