## 7 SUBJECT ENROLLMENT AND WITHDRAWAL

### 7.1 SUBJECT POPULATION

At least 145 subjects will be enrolled into the study. At least 5 of these subjects will be treated with CORI directly to fulfil the learning needs of the surgeons prior to enrolling, a further 140 subjects who will be enrolled in the randomized stage of the study in up to 8 sites in Australia, Hong Kong, New Zealand, South Korea, and China mainland. Seventy (70) subjects will be enrolled for UKA with the use of the CORI and 70 subjects will be enrolled for UKA with the use of conventional manual instrumentation. Vulnerable subjects will not be enrolled in this study.

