#### CONFIDENTIAL AND PROPRIETARY

This document contains information that is confidential and proprietary to Smith & Nephew PLC and Smith & Nephew, Inc. and is intended for use only by Smith+Nephew and its manufacturer. It shall not be reproduced or copied in whole or in part, nor shall the contents be disclosed by any means without prior written permission from Smith+Nephew, nor shall anyone make any use of it that is contrary to the expressed or implied wishes of Smith+Nephew.

Clinical Protocol	Study Number: CORI.2019.06
A Prospective, Multi-center, Randomized Controlled Study to Evaluate the Safety and Effectiveness of REAL INTELLIGENCE™ CORI™ in unicondylar knee arthroplasty (UKA) Procedure	Version: 4.0-Master, 07 Sep 2022
	Page: 78 of 167

product in China) with the use of CORI or conventional manual instrumentation.

- Intent-to-Treat Population (ITT): The ITT population is a subset of the randomized population which is defined as subjects randomized to either CORI or conventional manual instrumentation groups who have at least one post-operative assessment on any of the effectiveness endpoints or health-related quality of life (HRQoL) endpoints. Data summarized on the ITT population will be based on the intervention the subject was randomized to receive which may be different from the intervention the subject actually received.
- Per-Protocol Population (PP): The PP population is a subset of subjects in the FAS population who do not have major protocol deviations and who satisfied all enrollment eligibility criteria. Major protocol deviations will include but not only restricted to subjects enrolled who do not satisfy the study entry eligibility criteria. All other criteria that will be categorized as major deviations will be formally classified on a case-by-case basis prior to the final study database lock.

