## 10.5 SAFETY ANALYSES

All safety analyses will be summarized separately for each of the groups (i.e. CORI Navigational and Conventional manual instrumentation groups) as follows:

- The number of adverse events will be reported by seriousness, relationship to study device and anticipation.
- The number of subjects experiencing adverse events will be summarised by seriousness, relationship to study device and anticipation.
- An overall AE summary table that will summarize as number (n) and percentages (%), the overall incidence according to subjects with at least one AE; subjects with at least one AE by worst severity (mild, moderate, or severe); subjects with at least one AE by worst outcome (resolved, ongoing/unresolved, or death); subjects with an AE that led to study discontinuation) and; subjects with at least one AE by worse relatedness to device. Other events such as SAEs, ADEs, SADEs or UADEs will also be similarly summarized using the number (n) and percentages (%).
- Incidence of device-related re-interventions that occur on-study will be summarized as number (n) and percentages as well as by type.
- A listing of device deficiencies that occur on-study will be provided.
- Knee implant revision rate will be summarized as proportions with 95% CIs estimated using exact binomial methods.

All safety endpoints will be summarized using the SAF analysis population.

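### As written, the safety tables pool non-randomised China training cases with the randomised CORI arm, so the descriptive safety comparison is not purely randomised

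*Protocol*

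**What the plan says.** Protocol section 7.1 sets up a training stage ahead of the 140 randomised subjects: "At least 5 of these subjects will be treated with CORI directly to fulfil the learning needs of the surgeons prior to enrolling". Sections 8.1 and 11 repeat this. Section 6.5 leaves the count open: "The exact number of pre-study cases may be adjusted depending on the level of the individual experience of the surgeon". It also says that case report forms from the non-randomised cases go into the safety analysis set at sites in China only.

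Section 10.2 defines the safety population as subjects treated for UKA and adds in parentheses "include non-randomized subjects in China as CORI is a pre-market", continuing "product in China) with the use of CORI or conventional manual instrumentation".

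Section 10.5 fixes the layout: "All safety analyses will be summarized separately for each of the groups (i.e. CORI Navigational and Conventional manual instrumentation groups". It closes with "All safety endpoints will be summarized using the SAF analysis population". Its content is descriptive: counts and percentages of adverse events and re-interventions, a listing of device deficiencies, and the knee implant revision rate with an exact 95% interval. Section 5.2 makes safety relative to conventional instruments, to 12 months, a secondary objective.

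The SAP was written after early termination. It replaces the protocol's analyses with listings for the four enrolled subjects (SAP sections 2, 7.1 and 7.15), with a list of adverse events as the safety output (7.13). It says the listings will allow the protocol's analysis populations to be identified (7.2).

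**The concern.** Randomisation makes the two arms comparable. Training cases are not randomised, all receive CORI and have no conventional counterpart, so adding them changes one side of the comparison only. A difference between the columns could then reflect who was chosen for training, or how familiar the surgeon was with the system, as well as the instrumentation.

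The by-group percentages are the only evidence that the protocol plans for its comparative safety objective, so it matters who is in them. The revision rate matters most: it is the one safety endpoint with a planned confidence interval, and a single event can move a rare-event estimate visibly.

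The CORI column also serves neither purpose cleanly. It is larger than the randomised arm, but it is not total CORI exposure, because training cases from outside China do not enter it.

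**Working it through.** **Planned numbers.** Section 11 gives 63 evaluable per group. The usual two-sided 5% formula for 92.1% versus 73.4% at 80% power (pooled variance, no continuity correction) returns 63. Then 63/0.90 = 70 per group, and 70 + 70 + 5 = 145, the stated minimum enrolment. These figures size the alignment endpoint; the documents give none for safety.

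**Where the training cases go.**
1. All are treated with CORI (7.1, 8.1, 11).
2. Those in China are in the safety population (10.2, 6.5).
3. All safety endpoints use that population, in two groups (10.5).
4. A CORI-treated subject cannot be placed in the conventional group. The protocol provides no third column, no randomised-only safety set and no sensitivity analysis without these cases.

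The placement in the CORI column is therefore an inference, but it is the only one that satisfies 10.2 and 10.5 together. The exclusion of training cases outside China rests on the parenthesis in 10.2 read with 6.5.

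**Share of the CORI column.** Let k be the number of China training cases, and assume that all 70 subjects allocated to CORI are treated with it. Share = k/(70 + k). The values of k are assumed.

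- k = 0: 0%
- k = 5: 5/75 = 6.7%
- k = 10: 10/80 = 12.5%
- k = 20: 20/90 = 22.2%
- k = 40: 40/110 = 36.4%

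**Effect on an event rate.** Displayed rate = (70·p_r + k·p_t)/(70 + k), with p_r the randomised CORI rate and p_t the training rate. The documents give neither rate, so all values are assumed.

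- p_r = 10%, p_t = 20% to 30%, k = 5: (7 + 1)/75 = 10.7% to (7 + 1.5)/75 = 11.3%
- Same rates, k = 20: (7 + 4)/90 = 12.2% to (7 + 6)/90 = 14.4%
- p_r = 20%, p_t = 40% to 60%, k = 5: (14 + 2)/75 = 21.3% to (14 + 3)/75 = 22.7%
- Same rates, k = 20: (14 + 8)/90 = 24.4% to (14 + 12)/90 = 28.9%
- p_t = p_r: no shift
- p_r = 10%, p_t = 0%, k = 5: 7/75 = 9.3%, a shift the other way

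**Revision rate.** Exact (Clopper-Pearson) limits: lower = the 2.5% point of Beta(x, n − x + 1); upper = the 97.5% point of Beta(x + 1, n − x). With k = 5 (assumed):

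- Randomised arm 0/70: 0%, upper limit 5.1%. One training revision makes it 1/75 = 1.3%, upper limit 7.2%. No training revision makes it 0/75, upper limit 4.8%.
- Randomised arm 1/70: 1.4% (0.04% to 7.7%). One training revision makes it 2/75 = 2.7% (0.3% to 9.3%). None makes it 1/75 = 1.3% (0.03% to 7.2%).

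In each case the reported interval changes while the randomised arm does not.

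**The case against.** Four points can fairly be made for the plan.

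*Reporting all exposure to a pre-market device is legitimate, and 10.2 gives that reason.* This stands. The inclusion is sound; the gap is that nothing separates these subjects when the arms are set side by side.

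*Section 10.5 never says that the training cases are merged with the randomised arm, and 8.1 describes a distinct pre-randomised stage.* The first part is true. But 10.5 offers only two groups and requires the whole safety population, so silence leads to pooling unless someone decides otherwise at the analysis.

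*The effect is probably small.* At k = 5, even a training risk two to three times an assumed 20% moves the column by 1.3 to 2.7 points, against a 95% half-width of about 1.96·√(0.2·0.8/75) = 9 points. This stands for a handful of cases. The protocol sets no maximum, however, so it does not ensure that the number stays small.

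*The SAP has overtaken the question.* This stands for the tables: with listings for four subjects, no pooled column will be produced. It does not repair the protocol text, and the listings still need to show who was randomised.

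A reader might also infer that at least 5 of 75 CORI subjects are training cases. The documents do not support that: the minimum of 5 applies to the whole study, only China cases enter the safety set, and the China count is not given. It could be zero. Nor do they say that these are the surgeons' first uses. Section 6.5 requires participating surgeons to be familiar with CORI and to have documented training and expertise.

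**Conclusion.** The point holds for the protocol as written, in a limited form: the descriptive CORI versus conventional safety comparison is not purely randomised, and the CORI column is not all CORI-treated subjects. The non-randomised share is 0% with no China training cases, 6.7% with 5 and 22.2% with 20. These are scenarios, not bounds, and they assume that all 70 randomised CORI subjects are treated as allocated.

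A reader might go further and call the safety comparison non-randomised, or biased against CORI. Neither follows. In the 5-case scenario 70 of 75 subjects are still randomised, and the direction of any bias depends on event rates that the documents do not give. No between-arm safety test is planned, so no p-value or error rate is affected. In this trial the practical consequence is now confined to how the listings are labelled.

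**What to change.** In protocol sections 10.2 and 10.5:

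- Keep the safety population as the record of total exposure.
- Show randomised CORI, randomised conventional and CORI training cases in separate columns, with an all-CORI-treated total for the regulator. For that total to be complete, it must include training cases from every country.
- State that arm comparisons, including the revision-rate interval, use randomised treated subjects.

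In the SAP listings, flag each subject as randomised or training. This fits the SAP's statement that the listings will identify the analysis populations.

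The cost is one or two table columns and one listing variable. There is no added burden on patients. Including training cases from outside China does require their safety data to be held in the study database.

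If the design is used again, state the number of training cases planned per country, so that the non-randomised share is known in advance.

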#### CONFIDENTIAL AND PROPRIETARY

This document contains information that is confidential and proprietary to Smith & Nephew PLC and Smith & Nephew, Inc. and is intended for use only by Smith+Nephew and its manufacturer. It shall not be reproduced or copied in whole or in part, nor shall the contents be disclosed by any means without prior written permission from Smith+Nephew, nor shall anyone make any use of it that is contrary to the expressed or implied wishes of Smith+Nephew.

Clinical Protocol	Study Number: CORI.2019.06
A Prospective, Multi-center, Randomized Controlled Study to Evaluate the Safety and Effectiveness of REAL INTELLIGENCE™ CORI™ in unicondylar knee arthroplasty (UKA) Procedure	Version: 4.0-Master, 07 Sep 2022
	Page: 78 of 167

product in China) with the use of CORI or conventional manual instrumentation.

- Intent-to-Treat Population (ITT): The ITT population is a subset of the randomized population which is defined as subjects randomized to either CORI or conventional manual instrumentation groups who have at least one post-operative assessment on any of the effectiveness endpoints or health-related quality of life (HRQoL) endpoints. Data summarized on the ITT population will be based on the intervention the subject was randomized to receive which may be different from the intervention the subject actually received.
- Per-Protocol Population (PP): The PP population is a subset of subjects in the FAS population who do not have major protocol deviations and who satisfied all enrollment eligibility criteria. Major protocol deviations will include but not only restricted to subjects enrolled who do not satisfy the study entry eligibility criteria. All other criteria that will be categorized as major deviations will be formally classified on a case-by-case basis prior to the final study database lock.

### 10.3 BASELINE DATA

All observations available prior to the operative date will be defined as baseline (or preoperative) data. All demographic and pre-operative characteristics data will be summarized at baseline. All demographic and baseline characteristics will be summarized using the enrolled SAF, ITT and PP analysis populations.

### 10.4 EFFECTIVENESS ANALYSIS

#### 10.4.1 Analysis of Primary Endpoint

##### Leg alignment

##### CONFIDENTIAL AND PROPRIETARY

This document contains information that is confidential and proprietary to Smith & Nephew PLC and Smith & Nephew, Inc. and is intended for use only by Smith+Nephew and its manufacturer. It shall not be reproduced or copied in whole or in part, nor shall the contents be disclosed by any means without prior written permission from Smith+Nephew, nor shall anyone make any use of it that is contrary to the expressed or implied wishes of Smith+Nephew.

TMP-CD-05-01 Clinical Protocol - Device - Revision D; SOP-CD-05 Clinical Protocol

Clinical Protocol	Study Number: CORI.2019.06
A Prospective, Multi-center, Randomized Controlled Study to Evaluate the Safety and Effectiveness of REAL INTELLIGENCE™ CORI™ in unicondylar knee arthroplasty (UKA) Procedure	Version: 4.0-Master, 07 Sep 2022
	Page: 79 of 167

The primary endpoint, the proportion of knees achieving post-operative leg alignment, defined as  $\pm 3^\circ$  from the target (pre-operative planned leg alignment) assessed at the 6 weeks study visit in CORI UKA ( $\pi_1$ ) and conventional manual instrumentation UKA ( $\pi_0$ ) groups.

The hypotheses are as follows:

- $H_0(\text{null})$ :  $\pi_1 \leq \pi_0$  versus
- $H_1(\text{alternate})$ :  $\pi_1 > \pi_0$ .

The proportions as described above will be supported with the use of a two-sided 95% confidence intervals (CI), estimated using exact binomial methods.

Superiority of  $\pi_1$  over  $\pi_0$  will be inferred if and only if the lower limit of the 95% CI for  $\pi_1$  is greater than the upper limit of the 95% CI for  $\pi_0$ .

As supportive analysis on the primary endpoint, the difference between the target and actual leg alignment achieved postoperatively will be summarized for each group (i.e. CORI UKA and the Conventional manual instrumentation UKA) using summary statistics for continuous variables. Ninety-five (95) % CIs based on the Student's t-distribution will be calculated for the means.

The primary endpoint and the supportive analysis will be summarized using the FAS analysis population as primary and then PP analysis population for sensitivity.

For missing primary endpoint data, the Missing Value Treated as Failure (MVTF) missing value imputation method will be used. This is considered a conservative imputation method as all missing data on the primary endpoint will be considered as a failure, i.e. not attaining the pre-specified target alignment. More specific details of this imputation method will be included in the SAP.

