### 9.1.2 Screening/Pre-operative Visit

1. Obtain written informed consent from the subject as detailed in Section 7.5.  
----- ***Do not proceed until the consent has been obtained*** -----
2. Obtain demographic information and medical history, including information on all concomitant medications/therapies.
3. Screen the subject for protocol inclusion/exclusion criteria.
4. The eCRF will assign the subject a study number. The subject identification log shall be completed accordingly.
5. Instruct the subject on treatment procedures.
6. Collect radiographic images of the affected knee for evaluation of leg alignment (Standing weight bearing A/P long leg X-ray).
7. Collect the 2011 KSS score objective measures (joint alignment, instability, motions & symptoms).
8. Have the subject complete the 2011 KSS score subject questions.
9. Have the subject complete the OKS patient-reported outcome measure.
10. Have the subject complete the EQ-5D-5L patient-reported outcome measure.
11. The subject will be randomized to treatment group (CORI or Manual conventional instrumentation).
12. Subjects will be instructed to return for the Operation Visit on a scheduled date.

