### Pre-Operative Leg alignment

The pre-operative leg alignment evaluated from a standing weight bearing long leg standing A/P shall be recorded.

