### 10.1 GENERAL

S+N's Global Biostatistics group will conduct the statistical analysis for this study. Unless otherwise stated, all significance tests and hypothesis testing will be two-sided, performed at the 5% significance level. Resulting p-values will be quoted and 95% two-sided confidence intervals will be generated where appropriate. Where data summaries are specified, categorical and ordinal variables will be summarized with frequencies and percentages. Continuous variables will be summarized with the following summary statistics: the number of observations, mean, median, standard deviation, minimum and maximum values.

All statistical comparisons of data will describe the test statistic used as well as its distributional assumptions. For continuous variables, in an event of marked deviation from normality assumption, a commensurate non-parametric test would be used as an alternative thereby eliminating the possibility of violation of normality assumptions. All analyses will be performed using SAS version 9.3 (or a later version).

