## 11 SAMPLE SIZE JUSTIFICATION

Parratte et al.[51] looked at the effects of postoperative mechanical axis alignment on the survival of TKAs. They found that of the 398 TKAs reviewed in the paper there were 292 (73.4%) which post-operatively were defined as mechanically aligned (i.e. with a mechanical axis of  $0^\circ \pm 3^\circ$ ).

This study is designed to demonstrate superiority in the proportion of knees achieving post-operative leg alignment in the CORI Navigational group over the Conventional manual instrumentation group.

The proportion of mechanically aligned TKAs using NAVIO from a recent analysis was estimated to be 92.1% [52]. This proportion is expected to be equivalent if NAVIO was used to determine the proportion of mechanically aligned UKAs. Using these assumptions, enrollment of 63 UKAs per group will provide 80% power to show that the lower limit of the two-sided 95% confidence interval for the proportion of mechanically aligned UKAs is greater than that obtained from literature. To account for up to a 10% attrition rate in knees enrolled, 70 knees in each group (140 knees combined) will be enrolled into the randomized stage of the study. A minimum of an additional 5 subjects who will be treated with CORI directly to fulfil the learning needs of the surgeons will be enrolled at the pre-randomized study stage, thus leading to a minimum total study enrollment of 145 subjects.

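### Section 10.4.1 plans no between-arm estimate for leg alignment and adjusts for neither pre-operative alignment nor site, giving up precision of a size the documents do not fix

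*Protocol*

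**What the plan says.** **Primary analysis (Protocol 10.4.1).** The endpoint is the proportion of knees within 3 degrees of the planned alignment at 6 weeks. Of the two proportions the section says: "The proportions as described above will be supported with the use of a two-sided 95% confidence intervals (CI), estimated using exact binomial methods". Superiority is inferred only if the lower limit for CORI lies above the upper limit for conventional instruments.

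**Supportive analysis (10.4.1).** The difference between target and achieved alignment "will be summarized for each group (i.e. CORI UKA and the Conventional manual instrumentation UKA) using summary statistics for continuous variables", with a t-based interval for each group mean. No between-arm difference and no covariate appears in either analysis.

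**What is available.** Step 6 of the pre-operative visit (9.1.2) reads "Collect radiographic images of the affected knee for evaluation of leg alignment (Standing weight bearing A/P long leg X-ray"; randomisation is step 11 of the same visit. Section 9.2.1 adds: "The pre-operative leg alignment evaluated from a standing weight bearing long leg standing A/P shall be recorded". That measurement is the angular deviation from neutral, 180 degrees. The endpoint's reference is a different quantity, the subject's own plan, which 9.2.1 says need not be neutral.

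**Randomisation.** Section 8.2.1 blocks by site. Pre-operative alignment is not a stratification factor.

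**Elsewhere.** Section 10.4.2 models KSS, and by analogy OKS, FJS-12 and EQ-5D-5L, with site and pre-operative covariates.

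**SAP.** Section 2 records early termination with four subjects. Section 7.1 replaces the protocol analyses with listings, and 7.10 marks the primary analysis not applicable.

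**The concern.** The endpoint that decides superiority gets a barer analysis than the patient-reported scores. Two per-arm intervals answer no comparative question directly, and they cannot carry a covariate. The plan therefore has no estimate of the treatment effect with its own interval, no use of the factor that structured the randomisation, and no pre-specified adjusted answer if the arms happen to differ in deformity.

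A knee needing more correction may be likelier to miss its plan. If so, pre-operative deformity is a prognostic variable already in hand, and adjusting for it would narrow the interval at no data cost. The documents do not state that link, so it is a premise to allow for and not a fact to rely on.

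**Working it through.** **Inputs.** Section 10.1: "all significance tests and hypothesis testing will be two-sided, performed at the 5% significance level". Section 11: conventional rate 292/398 = 73.4%; CORI rate "from a recent analysis was estimated to be 92.1"%, from the predecessor device in total knee arthroplasty; "enrollment of 63 UKAs per group will provide 80% power"; "To account for up to a 10% attrition rate in knees enrolled, 70 knees in each group". Sites: up to 8. The prognostic strength of pre-operative alignment is not given and is assumed below.

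**1. The plan's own figure.** Two-sided two-proportion formula with pooled variance under the null:
- mean rate (0.921 + 0.734)/2 = 0.8275; difference d = 0.187
- 1.960 × √(2 × 0.8275 × 0.1725) = 1.047
- 0.842 × √(0.921 × 0.079 + 0.734 × 0.266) = 0.436
- n = (1.047 + 0.436)² / 0.187² = 62.9, so 63 per group (power 80.1%)
- 63/0.9 = 70 per group (power 84.1%)

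The stated size reproduces as an unadjusted two-sample comparison.

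**2. The rule actually planned.** Exact enumeration of non-overlapping 95% Clopper-Pearson intervals gives power of 43.1% at 63 per group and 51.3% at 70. The one-sided type I error is about 0.0015. About 115 per group would be needed for 80%.

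**3. Risk difference, with and without adjustment, at 70 per group.** Unadjusted SE = √[(0.0728 + 0.1952)/70] = 0.0619, and Wald power = Φ(0.187/0.0619 − 1.96) = 85.6%. If baseline explains a share R² of the outcome variance, the SE is multiplied by √(1 − R²):

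| Assumed R² | SE | CI width | Power |
|---|---|---|---|
| 0 | 0.0619 | unchanged | 85.6% |
| 1% | 0.0616 | −0.5% | 85.9% |
| 5% | 0.0603 | −2.5% | 87.3% |
| 10% | 0.0587 | −5.1% | 89.0% |
| 25% | 0.0536 | −13.4% | 93.7% |

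**4. The form of the covariate.** Simulation: the signed deviation correlates r with standardised pre-operative alignment Z, the SDs are 1.71 and 2.70 degrees (giving 92.1% and 73.4% within 3 degrees), and there are 70 per arm and 1,500 trials. Power of the standardised risk difference:

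| Assumed r | Unadjusted | Z only | Z and Z² |
|---|---|---|---|
| 0.5 | 85.2% | 86.1% | 87.9% |
| 0.7 | 86.4% | 87.3% | 92.4% |

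At r = 0.3 the gain is under 1 point. The signed linear term adds about 1 point whatever r is, so that gain does not reflect prognostic strength. In this model misses fall on both sides of the target, and the chance of a miss depends on the magnitude of Z.

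**5. Supportive analysis.** In the same symmetric model the absolute deviation is uncorrelated with signed Z, so a signed covariate removes no variance. With the magnitude of Z as covariate, the within-arm correlation is [√(1 − r²) + r·arcsin(r) − 1]/(π/2 − 1) = 0.08, 0.22 and 0.45 at r = 0.3, 0.5 and 0.7. Squared, the variance removed is 0.6%, 5% and 20%.

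**6. Stability of the logistic model.** Expected failures with no missing data are 70 × 0.079 + 70 × 0.266 = 5.5 + 18.6 = 24.2. Arm, 7 site contrasts and one deformity term make 9 slopes, about 2.7 failures each. With 8 equal sites (8.75 knees per arm), a given site has no failures with probability (0.921 × 0.734)^8.75 = 0.033. At least one site has none with probability 1 − 0.967⁸ = about 23%, which would leave that site's effect inestimable by ordinary maximum likelihood.

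**The case against.** The case for leaving the plan alone has force, and much of it stands.

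- **An unadjusted analysis of a randomised trial is valid.** This stands. A reader might note that with 70 per arm the chance of mean deformity differing by more than 0.2 SD is 2 × [1 − Φ(0.2/√(2/70))] = 24%, and infer a distorted result. That is ordinary sampling variation, which a valid interval already covers. Section 10.3 also has baseline characteristics summarised.
- **Pre-operative alignment is not the baseline value of the endpoint.** This stands. One is deviation from 180 degrees, the other deviation from a personal plan. The target already individualises the endpoint, so the covariate may explain little.
- **The gain is unknown.** This stands. The documents give no correlation, and zero is possible. Missing values count as failures (10.4.1), and those failures need not depend on deformity. Footnote 3 to the visit schedule also admits films taken 6 months before surgery.
- **A textbook saving does not carry over.** A reader might apply 1 − r² with r of 0.3 to 0.5 and claim a 9% to 25% variance cut, or 140/(1 − r²) − 140 = 14 to 47 subjects saved. That holds for the signed deviation only, not for the absolute deviation or the within-3-degrees endpoint.
- **Section 10.4.2 is an imperfect benchmark.** It selects covariates stepwise at p ≤ 0.1 and does not name alignment.
- **The point cannot affect this trial's results.** This stands, given four subjects and listings only.

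None of this supplies the missing between-arm estimate, or explains why the blocking factor and a measurement already required are left out.

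**Conclusion.** The point holds as a modest comment on the protocol's planned analysis. Section 10.4.1 has no between-arm estimate for alignment and uses neither site nor pre-operative deformity, although both are known before surgery. The cost is precision. It is nil if deformity does not predict missing the subject-specific target, and reaches about a 13% narrower interval if R² is as high as 25%. That range is assumed and rests on nothing in the documents.

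Two stronger readings should be resisted. The omission does not bias or invalidate the comparison. Nor does adjustment lift this trial from 86% power to some higher figure: 86% belongs to a risk-difference test, while the rule in 10.4.1 has about 51% at 70 per arm under the same rates. Replacing that rule with a single contrast matters more than the covariate does, and it is also what makes adjustment possible.

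**What to change.** For the protocol's planned analysis or any reuse of the design, amend 10.4.1 as follows:

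1. **Primary contrast.** Estimate one between-arm risk difference, standardised from a logistic model on arm, site and magnitude of pre-operative deformity, with a robust 95% CI. Enter magnitude as the absolute deviation from 180 degrees, or as alignment with a squared term. Infer superiority if the lower limit exceeds zero, in place of the non-overlap rule. Fix the covariates in advance, without stepwise selection.
2. **Sparse failures.** Pre-specify pooling of small sites or a penalised fit, since about 24 failures are expected over up to 8 sites.
3. **Supportive analysis.** Use an ANCOVA of the absolute deviation from target on arm, site and deformity magnitude, reporting one between-arm difference with its 95% CI.
4. **Sensitivity.** Keep the unadjusted proportions with their exact intervals.

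The cost is a few lines of protocol and SAP text and some analysis code. No new data are needed. For the four enrolled subjects the SAP's listings need no change on this account.
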